4.0 Test Schedule

Table 4.1: Test Schedule for Elderly Newly Diagnosed and Relapsed/Refractory AML patients

23

	Active Monitoring Phase					
Tests and procedures	≤14 days prior to registration	≤7 days prior to registration	Cycle 1 Days 1, 8, 15, & 28(+3 days) ^{5, 13}	Cycles 2 & 3 Days 1, 15, and 28 (+ 3 days) ^{5, 13}	Cycles 4+Day 1 and Beyond(+/-3 days) ^{5, 17}	EOS ²
History and exam, wt, PS, vitals	X		Х	X ¹³	X ¹³	Х
Height	Х					
Adverse event assessment	Х		Х	Х	X	Х
Hematology group WBC ANC Hgb PLT		X	х	х	X ⁹	х
Chemistry group: sodium, potassium, calcium, creatinine, bicarbonate, glucose, chloride, albumin, BUN, alkaline phosphatase, AST, ALT, total protein, total bilirubin, LDH		X	X	Х	Х	Х
TLS monitoring (for selected AML patients): BUN, calcium, CO2, chloride, creatinine, glucose, potassium, sodium, uric acid, phosphorus			X ¹⁴	X ¹⁴		

PT/PTT and D-dimer			X ¹⁹			
Serum pregnancy test ¹		Х				
Bone marrow biopsy and						
aspirate procedure	\mathbf{v}^{11}		\mathbf{v}^3	\mathbf{v}^3	\mathbf{v}^3	\mathbf{V}^{10}
(cytogenetics or FISH) ¹⁵	Λ		Λ	A	Λ	Λ
Bone marrow aspirate						
research specimens	X^8		X^7	\mathbf{X}^7	\mathbf{X}^7	X ⁶
(see Section 14.0) ^R						
Blood specimens (see	1.0					
Section $(14.0)^{R}$	X ^{4, 8}		X^4	X^4	X^4	X^4
Buccal swab (optional,	x					
see Section 14.0) ^K	 					
Patient Questionnaire	v		\mathbf{V}^{16}	V^{16}	V^{16}	\mathbf{V}^{16}
Booklet ¹²	Λ		Λ	Δ	Δ	Δ
ECG $(12 \text{ lead})^{18}$		X				X

1. For women of childbearing potential only.

2. 30 days (+/-3days) post last dose of study drug

3. For AML patients: marrow aspirates and biopsies will be done after cycle 1 (at physician's discretion), after cycles 2 and 4, and then at physician discretion). In addition, bone marrow should be performed at time of suspected CR/CRi and/or disease progression and at physician discretion as clinically indicated. Note: Bone Marrow Aspirate and biopsy may be avoided aftercycle 4 as determined by study chair or treating physician (i.e. if determined to not yield information that would change clinical management).

4. Blood specimens for research sampling to be collected as defined in Section 14.

5. Day 1 assessments do not need to be repeated if pre-registration or Day 28 assessments completed within 48 hours of Day 1.

6. Only if an EOS marrow sample is collected as part of standard of care

7. Research bone marrow samples are to be collected at the same time when a marrow is done as part of patient's standard of care, including research marrow samples should be drawn at time of marrow for suspected CR/CRi and/or disease progression.

8. To be collected on all patients at baseline. If no baseline marrow samples obtained, the peripheral blood research sample becomes mandatory to participate in study. Bone marrow aspirate specimens must be collected and submitted per section 14.0. If bone marrow performed at end of study as part of patient's standard of care, collect sample per section 14.0.

9. After 2 cycles, CBC frequency may be reduced at treating physician's discretion but needs to be performed at least once per cycle.

10. Progression marrow can be used as EOS marrow if patient is taken off trial based on the results. Additional EOS bone marrow can be omitted if a progression marrow was done, or an EOS marrow can be done at physician discretion and is optional.

11. ≤ 28 days prior to registration; for patients with an outside marrow biopsy within 4 weeks of study start, outside results can serve as baseline after review at Mayo Clinic. In these cases, samples for correlative laboratory studies will be drawn from peripheral blood prior to study start.

12. Patient questionnaire booklet must be used; copies are not acceptable for this submission. Booklet should be completed by patient prior to review of treatment response and discussions of patient's general health since last treatment evaluation.

- 13. Patients with AML will be monitored per Table 4.1 during cycle 1 and 2, and thereafter at least once per cycle, i.e. at end of each/prior to a new cycle or as otherwise defined in the test schedule.
- 14. For patients at high risk of tumor lysis syndrome (TLS), that is for selected AML patients as determined by the treating physician, a daily basic metabolic panel, uric acid, and phosphoruswill be drawn for three to five days in Cycle 1, when maximum TLS risk is usually abated. Additional monitoring will be done on a case by case basis.
- 15. Either conventional cytogenetics or FISH panel (or both based on physician discretion) for AML to be performed at baseline. If diploid cytogenetics at baseline, subsequent cytogenetic studies may be omitted unless disease progression is suspected. For FISH based cytogenetic assessments, an entire AML FISH panel should be performed at baseline, while on subsequent marrows only positive specific FISH abnormalities/probes need to be repeated unless disease progression is suspected, in which case a full AML FISH panel or instead conventional cytogenetics should be performed.
- 16. Booklets to be completed at end of all cycles.
- 17. Prior to the start of treatment.
- 18. ECG to be repeated if cardiac symptoms occur or as otherwise defined in the test schedule.
- 19. To be tested on C1D1 prior to treatment.
- R Research funded (see Section 19.0).

Table 4.2: Test Schedule for HMA failure MDS patients

			Active Monitoring Phase			
Tests and procedures	≤14 days prior to registration	≤7 days prior to registration	Cycles 1 Days 1, 8, 15, & 28(+3 days) ¹²	Cycle 2 Days 1, 15, and 28 (+ 3 days) ^{10, 12}	Cycles 3+ Day 1 and Beyond(+/-3 days) ^{10, 12}	EOS ²
History and exam, wt, PS, vitals	Х		X	Х	Х	Х
Height	Х					
Adverse event assessment	X		Х	Х	X	Х
Hematology group WBC ANC Hgb PLT		х	х	Х	Х	х
Chemistry group: sodium, potassium, calcium, creatinine, bicarbonate, glucose, chloride, albumin, BUN, alkaline phosphatase, AST, ALT, total protein, total bilirubin, LDH		X	X	Х	Х	X
Serum Erythropoietin level	Х					
Serum pregnancy test ¹		Х				
Bone marrow biopsy and aspirate procedure (cytogenetics or FISH ⁹)	X ⁶			X ³	X ³	X ⁷
Blood specimens (see Section 14.0) ^R	X ⁴		X^4	X^4	X^4	X^4
Buccal swab (see Section	Х					

14.0) ^R						
Bone marrow aspirate						
research specimens	X^6			X^5	X^5	X^5
(see Section 14.0) ^R						
Patient Questionnaire	\mathbf{v}		\mathbf{v}^{8}	\mathbf{v}^8	\mathbf{v}^8	v
Booklet ⁸	Λ		Λ	Λ	Λ	Λ
ECG $(12 \text{ lead})^{11}$		Х				Х

1. For women of childbearing potential only

2. 30 days (+/-3days) post last dose of study drug

3. Marrow biopsies only to be done at End of cycle 2, End of cycle 4, at time of suspected CR/CRi and thereafter at physician discretion as clinically indicated (i.e. disease progression).

4. Blood specimens for research sampling to be collected as defined in Section 14.

5. Research marrow samples (aspirates) to be done at times of clinical standard of care marrow tests at End of cycle 2, End of cycle 4, at time of suspected CR/CRi or disease progression and thereafter at physician discretion as clinically indicated. A sample will be obtained at end of study (EOS) if a bone marrow is performed as part of patient's standard of care; sample will be collected per section 14.0

6. ≤ 28 days prior to registration; for patients with an outside marrow biopsy within 4 weeks of study start, outside results can serve as baseline after review at Mayo Clinic. In these cases, samples for correlative laboratory studies will be drawn from peripheral blood prior to study start.

7. Bone marrow at end of study is only to be done at physician discretion and is optional. Progression marrow can be used as EOS marrow if patient is taken off trial based on the results.

8. Patient questionnaire booklet must be used; copies are not acceptable for this submission. Booklet should be completed by patient prior to review of treatment response and discussions of patient's general health since last treatment evaluation. Booklets to be completed at end of all cycles.

9. Either conventional cytogenetics or FISH panel (or both based on physician discretion) for MDS should be performed at baseline. If diploid cytogenetics at baseline subsequent cytogenetic studies may be omitted unless disease progression is suspected. For FISH based cytogenetic assessments, an entire MDS FISH panel should be performed at baseline, while on subsequent marrows only positive specific FISH abnormalities/probes need to be repeated unless disease progression is suspected.

10. Prior to the start of treatment.

11. ECG to be repeated if cardiac symptoms occur or as otherwise defined in the test schedule.

12. Day 1 assessments do not need to be repeated if pre-registration or Day 28 assessments completed within 48 hours of Day 1.

R Research funded (see Section 19.0).

5.0 Grouping Factors:

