Cardiac disorders (tachycardia, palpitations, QTc prolongation) and gastrointestinal haemorrhage were not observed frequently, but are considered to be important potential risks.

The single-dose maximum tolerated dose (MTD) for both the gemcitabine and cisplatin combination therapies was 200 mg of AZD1775. Dose-limiting toxicities (DLTs) tended to be hematological in nature (i.e. leukopenia, neutropenia and thrombocytopenia) in the gemcitabine group and constitutional (i.e. diarrhea and dehydration) in the cisplatin group. The single-dose MTD for the combination with carboplatin was 325 mg of AZD1775. DLTs in this group were related to serum chemistry.

Hematologic DLTs were most commonly observed in the multiple-dose AZD1775 combination treatment groups with gemcitabine and cisplatin. An MTD of AZD1775 in combination with gemcitabine was established with a dose of 175 mg QD x 2 days during Week 1 with gemcitabine 1000 mg/m2 once weekly for 3 consecutive weeks, every 4 weeks. Two DLTs (grade 3 febrile neutropenia and grade 3 aspartate aminotransferase and alanine aminotransferase (AST/ALT) increase) were observed at 200 mg once daily for 2 days with the regimen in combination with gemcitabine. The dose was adjusted to 175 mg once daily for 2 days, and one DLT has been reported to date. The MTD for combination with cisplatin has been exceeded at the 250 mg dose level, and tolerability of the MTD at 200 mg BID has been confirmed. DLTs observed in the multiple-dose carboplatin combination have been both hematological and constitutional in nature. The multiple-dose MTD in combination with carboplatin is AZD1775 225 mg BID.

The MTD for AZD1775 in combination with 5-FU was not reached due to early study termination. DLTs of encephalopathy and hyponatraemia were observed in the AZD1775 20 mg BID in combination with 1000 mg/m2 5-FU treatment group.

Triplet-based therapy was administered in the study PN004 with AZD1775, carboplatin, and paclitaxel. The starting dose of 225 mg AZD1775 (BID for 5 total doses) in Part 1 was generally well tolerated. One patient experienced a DLT in the first six patients treated and the dose remained at 225 mg BID 2.5 days. A total of 15 patients were treated, with 3 DLTs being reported (grade 3 and 4 febrile neutropenia and grade 4 thrombocytopenia). The study expanded to Part 2 and is ongoing. Other toxicities were generally blood and lymphatic system disorders and gastrointestinal.

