1.43 Clinical Pharmacokinetics and pharmacodynamics

Clinical Pharmacokinetics

The PK data of AZD1775 following a single oral administration showed a moderate rate of absorption with a Tmax occurring at 3 to 4 hours. Post-peak plasma concentrations declined essentially in a mono-exponential manner with a t1/2 in the region of 10 hours. Exposure as measured by maximum plasma drug concentration observed (Cmax) and area under the curve (AUC $0-\infty$) increased in a dose-proportional manner over the dose range of 325 to 1300 mg. The urinary excretion of AZD1775 was investigated after single-oral-dose monotherapy at 325, 650, and 1300 mg of AZD1775. The mean percent of total AZD1775

excreted unchanged in urine over a 24-hour period was 5.15% to 11.9%, which is comparable to what was observed in preclinical species (urinary excretion as unchanged drug in rats and dogs were ~8.6% and 11.8% of the dose, respectively, over a 48-hour collection interval). The mean renal clearance of AZD1775 at 325 mg was approximately 2.30 L/hour (38.3 mL/minute), below that expected due to filtration alone (based on an AZD1775 unbound fraction of 39.5% and a typical glomerular filtration rate of 120 mL/minute) of 47.4 mL/minute, indicating that net reabsorption appeared to be taking place. Overall, the results suggest that urinary excretion is not the major route of AZD1775 elimination

Following single (100 to 325 mg) and multiple dose administrations of AZD1775 (25 to 325 mg BID and 100 to 200 mg once daily [QD]) with carboplatin, cisplatin, and gemcitabine, plasma exposure of AZD1775 was consistent with predictions based on the single-dose regimen. The median Tmax values were between 1.02 and 4.25 hours. Given a t1/2 of approximately 10 hours, steady-state was expected to be achieved after approximately 3 days of AZD1775 treatment in adult patients. Accumulation ratios for AZD1775 BID doses (geometric mean ratio = Day 3/Day 1) for the area under the plasma-concentration time curve from time 0 to 8 hours post dose (AUC_{0-8hr}), Cmax, and plasma drug concentration observed at 8 hours post dose (C_{8hr}) averaged 0.991 to 3.82, 0.928 to 3.32, and 1.01 to 2.98, respectively, across tested AZD1775 BID doses in combination with gemcitabine, cisplatin, and carboplatin.

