- 3.29e Corrected QT interval (QTc) >470 msec (as calculated per institutional standards) at study entry or congenital long QT syndrome.

MC1488

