6.3 Safety & Expansion Portions

6.31 Correlative Research

A mandatory correlative research component is part of this study, the patient will be automatically registered onto this component (see Section 3.17 and 14.0).

- 6.32 Prior to accepting the registration, registration/randomization application will verify the following:
 - IRB approval at the registering institution
 - Patient eligibility
 - Existence of a signed consent form
 - Existence of a signed authorization for use and disclosure of protected health information
- 6.33 Documentation of IRB approval must be on file in the Registration Office before an investigator may register any patients.

In addition to submitting initial IRB approval documents, ongoing IRB approval documentation must be on file (no less than annually) at the Registration Office If the necessary documentation is not submitted in advance of attempting patient registration, the registration will not be accepted and the patient may not be enrolled in the protocol until the situation is resolved.

When the study has been permanently closed to patient enrollment, submission of annual IRB approvals to the Registration Office is no longer necessary.

- 6.34 At the time of registration, the following will be recorded:
 - Patient has/has not given permission to store and use his/her sample(s) for future research of Acute Myeloid Leukemia or Myelodysplastic Syndrome at Mayo.
 - Patient has/has not given permission to store and use his/her sample(s) for future research to learn, prevent, or treat other health problems.
- 6.35 Treatment on this protocol must commence at a participating institution, Mayo Clinic Rochester, Mayo Clinic Arizona, Mayo Clinic Florida, or the University of Colorado, under the supervision of a hematologist.
- 6.36 Treatment cannot begin prior to registration and must begin \leq 14 days after registration.
- 6.37 Pretreatment tests/procedures (see Section 4.0) must be completed within the guidelines specified on the test schedule.

- 6.38 All required baseline symptoms (see Section 10.3) must be documented and graded.
- 6.39a Study drug is available on site.
- 6.39b Blood draw kit is available on site.
- 6.39c Patient questionnaire booklet is available on site; copies are not acceptable for this submission.
- 6.39d Randomization Procedures
 - 6.39d1 The factors defined in Section 5.0, together with the registering membership, will be used as stratification factors.

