 - 6.39d2 After the patient has been registered into the study, the values of the grouping factors will be recorded. An elderly newly diagnosed AML patient will be allocated to arm A. A relapsed/refractory AML or HMA failure MDS patient will be randomized to treatment group arm B or arm C.
 - Elderly (age 60+) newly diagnosed AML patients assigned to Arm A: AZD1775 days 1-5, 8-12 and AraC days 1-5, 8-12
 - Relapsed/Refractory AML and HMA failure MDS patients randomized to Arm B: AZD1775 days 1-5, 8-12 and AraC days 1-5, 8-12 or Arm C: AZD1775 days 1-5, 8-12, 15-19, 22-26.

All patients must be registered within 14 days before starting therapy or within 72 hours after starting treatment if over a weekend or holiday. If therapy must be started when the MCCC Registration Office is closed, a telephone call must be made when the MCCC Registration Office is open as indicated above. Under no circumstances will non-registered patients be retrospectively eligible for the study.

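### No ECG is scheduled while patients are taking AZD1775, although the protocol names QTc prolongation as an important potential risk

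*Combined protocol and SAP*

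**What the plan says.** All references are to the combined protocol and SAP.

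- **Risk.** Section 1.41: "Cardiac disorders (tachycardia, palpitations, QTc prolongation) and gastrointestinal haemorrhage were not observed frequently, but are considered to be important potential risks".
- **Entry.** Exclusion 3.29e: "Corrected QT interval (QTc) >470 msec (as calculated per institutional standards) at study entry or congenital long QT syndrome".
- **Schedule.** In both Table 4.1 (AML) and Table 4.2 (MDS) the ECG row is marked in two columns, "≤7 days prior to registration" and EOS. Footnote 2 of each table places EOS at "30 days (+/-3days) post last dose of study drug". Every treatment-cycle column is blank in that row.
- **Repeat ECG.** Footnote 18 of Table 4.1 and footnote 11 of Table 4.2: "ECG to be repeated if cardiac symptoms occur or as otherwise defined in the test schedule".
- **Pharmacokinetics.** Section 1.43: "Post-peak plasma concentrations declined essentially in a mono-exponential manner with a t1/2 in the region of 10 hours". It also gives a Tmax of 3 to 4 hours after a single oral dose and about 3 days to steady state. Section 1.51 gives a half-life of about 9 hours.
- **Existing visit.** Section 14.1 has mandatory PK sampling on Cycle 1 Day 5 (window +1 day), before the dose and at 1, 2, 4, 6 and 8 hours after it. No ECG is attached.
- **Analysis.** Section 16.41 tabulates adverse events by maximum grade. No QTc summary is planned. Under 10.13 an abnormal test result is an adverse event only if it causes signs or symptoms or needs therapy.

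**The concern.** The protocol treats QTc as something to be measured: it is a named risk and a numerical entry limit, and the limit applies whether or not the patient has symptoms. QTc prolongation can be symptom-free, so a symptom trigger does not replace a scheduled reading. If both scheduled readings are off drug, a before-and-after comparison of them says nothing about what AZD1775 does to QTc during exposure. Safety and tolerability is secondary goal 2.21, and for this risk the goal would have no planned data. The practical danger is that a report with few or no QTc events is read as absence of an effect when it reflects absence of measurement.

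**Working it through.** The plan states no figure on this point, so there is none to reproduce. The check has four steps.

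**1. Count the scheduled ECGs during treatment.** Reading the ECG row across the columns gives 0 in Table 4.1 and 0 in Table 4.2. The two tables show the same pattern, which makes a text-extraction error unlikely. The footnote's reference to times defined elsewhere in the schedule leads nowhere, because neither table defines another time.

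**2. Drug remaining at the EOS ECG.** Inputs: EOS at 27, 30 or 33 days; half-life 10 h (1.43) or 9 h (1.51). With mono-exponential decline, the number of half-lives is n = days × 24 / half-life, and the fraction left is 2^(−n).

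| Half-life | Day 27 | Day 30 | Day 33 |
|---|---|---|---|
| 10 h | 64.8 (3 × 10⁻²⁰ left) | 72.0 (2 × 10⁻²²) | 79.2 (1 × 10⁻²⁴) |
| 9 h | 72.0 | 80.0 | 88.0 |
| 40 h (assumed, four times the stated value) | 16.2 (0.0013%) | 18.0 | 19.8 |

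The 40 h row is a stress test and is not in the documents. The EOS reading is effectively drug-free in every row.

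**3. Would Cycle 1 Day 5 be on drug?** Three days is 72 / 10 = 7.2 half-lives, and 1 − 2^(−7.2) = 99.3% of steady state, which agrees with the protocol's statement. Day 5 is a dosing day in all three arms (7.2, 7.3), and the PK samples span the stated Tmax. The +1 day window matters. Day 6 is not a dosing day on the main schedules, and 24 hours after the peak the concentration would be 2^(−24/10) = 19% of peak.

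**4. Does anything else fill the gap?**
- The routine adverse-event list in 10.6 does not include QTc.
- The only cardiac row in the 8.3 dose-modification table is a general one at Grade 4 or higher.
- The baseline ECG normally precedes dosing, because 6.36 says "Treatment cannot begin prior to registration and must begin" no more than 14 days after registration. The closing paragraph of Section 6 nevertheless allows registration "within 72 hours after starting treatment if over a weekend or holiday". For such a patient an ECG timed against registration could fall after the first dose. That is a conflict to reconcile, not a planned on-drug measurement.

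**The case against.** The strongest defence is that this was a deliberate and proportionate choice. Section 1.41 says the cardiac events were infrequent. The protocol excludes long QTc and significant heart disease at entry (with discretion for heart disease), restricts CYP3A4-interacting drugs, checks potassium and calcium at scheduled visits, and repeats the ECG for cardiac symptoms. The fuller risk basis is in the Investigator's Brochure, which is not part of these documents. All of this stands as risk reduction, but none of it measures QTc on drug.

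Three stronger conclusions that a reader might draw are not supported:

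- **That the trial will show no QTc signal whatever the drug does.** Symptom-triggered ECGs are allowed, adverse events are assessed at each scheduled visit, and Grade 3 and 4 events are submitted regardless of attribution (10.612). Incidental ECGs may also find cases. The gap is confined to asymptomatic prolongation and to scheduled assessments.
- **That a Day 5 ECG would repair the run-in or the 16.82 stopping rule.** Under 10.13 an asymptomatic, untreated finding is still not an adverse event. Rule 16.82 counts only Grade 4 or higher, and the general Grade 3 DLT criterion in 7.4 requires failure to resolve within 7 days, which one ECG cannot show.
- **That permitted azoles raise exposure unchecked.** Section 1.43 reports a 40 to 60% rise with aprepitant, a moderate inhibitor, but aprepitant is prohibited and 3.29b ties azole use to a 25 to 75% AZD1775 reduction. Applying the moderate-inhibitor figures, a 25% reduction gives 0.75 × 1.4 to 0.75 × 1.6 = 1.05 to 1.20 times usual exposure, and a 50% reduction gives 0.70 to 0.80. Posaconazole is listed as a strong inhibitor and no figure is given for it. The point does not rest on azoles.

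Objections to the remedy also have force. Moving the EOS ECG gives up the only routine post-treatment reading, neither table has a Day 5 column, no listed case report form is specific to ECG or QTc, and 3.29e leaves the QTc correction method to each institution. The fix below allows for these.

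**Conclusion.** The concern holds in a limited form. No protocol-scheduled assessment can detect asymptomatic QTc prolongation during treatment, and secondary goal 2.21 has no planned on-drug QTc data. There are 0 scheduled on-treatment ECGs across a planned 67 to 102 patients (16.3), and the second ECG comes 65 to 79 half-lives after the last dose. This rests on the stated half-life of about 10 hours and on a QTc effect that follows drug concentration; the first assumption can be wrong by a factor of four without changing the result. Sample size, power, type I error and the primary endpoint are unaffected. The change is worth making because it turns an uninformative reading into an informative one without adding a procedure.

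**What to change.** Reconcile the ECG timing in Tables 4.1 and 4.2 with 1.41 and 1.43.

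- Move the already scheduled EOS ECG to the Cycle 1 Day 5 PK visit. Require that it be taken on a day AZD1775 is given, so that the +1 day window does not place it on a non-dosing Day 6, and pair it with a post-dose PK sample near the stated Tmax (the 4-hour sample is the natural one).
- Keep the baseline ECG and the symptom-triggered repeat. The EOS ECG may stay as optional. Either name the other times that footnotes 18 and 11 refer to, or delete that clause.
- Record QTc with the same correction method at both times within a patient.
- Add a descriptive summary of change in QTc from baseline alongside 16.41, reported separately from adverse events because of 10.13.
- Reconcile 6.36 with the 72-hour registration exception, so that the baseline ECG is clearly taken before the first dose.

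The cost is the loss of the routine off-drug ECG, a Day 5 entry in both tables and a QTc data field. The number of scheduled ECGs is unchanged and the visit already exists. The change concerns data collection only. Any action on a QTc value is for the sponsor to set.
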